	0.1	0.1	0.1	0.1	0.1	0.1	2	2
14	↑ FiO ₂	↑ PEEP	↑ PEEP					
	0.1	0.1	0.1	0.1	0.1	0.1	2	2
12	↑ FiO ₂	↑ FiO ₂	↑ FiO ₂	↑ FiO ₂	↑ PEEP	↑ PEEP	↑ PEEP	↑ PEEP
	0.1	0.1	0.1	0.1	2	2	2	2
10	↑ FiO ₂	↑ FiO ₂	↑ FiO ₂	↑ FiO ₂	↑ PEEP	↑ PEEP	↑ PEEP	↑ PEEP
	0.1	0.1	0.1	0.1	2	2	2	2
8	↑ FiO ₂	↑ FiO ₂	↑ PEEP					
	0.1	0.1	2	2	2	2	2	2
5	↑ FiO ₂ 0.1	↑ PEEP	↑ PEEP 3					

$PaO_2 = 68 - 80 \text{ or } SpO_2 93 - 95\%$

(Use PaO₂ if available, only use SpO₂ if PaO₂ not available)

PEEP	$FiO_2 = .3$	$FiO_2 = .4$	$FiO_2 = .5$	$FiO_2 = .6$	$FiO_2 = .7$	$FiO_2 = .8$	$FiO_2 = .9$	$FiO_2 = 1.0$
24	↑ FiO ₂ 0.1 ↓PEEP 2	Maintain						
22	↑ FiO ₂ 0.1 ↓PEEP 2	Maintain						
20	↑ FiO ₂ 0.1 ↓PEEP 2	Maintain						
18	↑ FiO ₂ 0.1 ↓PEEP 2	Maintain	Maintain					
16	↑ FiO ₂ 0.1 ↓PEEP 2	Maintain	↓ FiO ₂ 0.1 ↑PEEP 2					
14	↑ FiO ₂ 0.1 ↓PEEP 2	Maintain	Maintain	Maintain	↓ FiO ₂ 0.1 ↑PEEP 2			
12	↑ FiO ₂ 0.1 ↓PEEP 2	Maintain	↓ FiO ₂ 0.1 ↑PEEP 2	↓ FiO ₂ 0.1 ↑PEEP 2	↓ FiO ₂ 0.1 ↑ PEEP 2			
10	↑ FiO ₂ 0.1 ↓PEEP 2	↑ FiO ₂ 0.1 ↓PEEP 2	Maintain	Maintain	Maintain	↓ FiO ₂ 0.1 ↑PEEP 2	↓ FiO ₂ 0.1 ↑PEEP 2	↓ FiO ₂ 0.1 ↑PEEP 2
8	↑ FiO ₂ 0.1 ↓PEEP 2	Maintain	Maintain	↓ FiO ₂ 0.1 ↑PEEP 2				
5	Maintain	Maintain	↓ FiO ₂ 0.1 ↑PEEP 3					

$PaO_2 > 80 \text{ or } SpO_2 > 95\%$

(Use PaO₂ if available, only use SpO₂ if PaO₂ not available)

PEEP	$FiO_2 = .3$	$FiO_2 = .4$	$FiO_2 = .5$	$FiO_2 = .6$	$FiO_2 = .7$	$FiO_2 = .8$	$FiO_2 = .9$	$FiO_2 = 1.0$
24	↓ PEEP 2	↓ PEEP 2						
22	↓ PEEP 2	↓ PEEP 2						
20	↓ PEEP 2	↓ PEEP 2						
18	↓ PEEP 2	↓ PEEP 2	↓ FiO ₂ .1					
16	↓ PEEP 2	↓ PEEP 2	↓ FiO ₂ .1					
14	↓ PEEP 2	↓ PEEP 2	↓ PEEP 2	↓ PEEP 2	↓ PEEP 2	↓ FiO ₂ .1	↓ FiO ₂ .1	↓ FiO ₂ .1
12	↓ PEEP 2	↓ PEEP 2	↓ PEEP 2	↓ PEEP 2	↓ PEEP 2	↓ FiO ₂ .1	↓ FiO ₂ .1	↓ FiO ₂ .1
10	↓ PEEP 2	↓ PEEP 2	↓ PEEP 2	↓ FiO ₂ .1				
8	↓ PEEP 3	↓ PEEP 3	↓ FiO ₂ .1					
5	Maintain	↓ FiO ₂ .1

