Figure 3. Initial Tidal Volume on Initiation of Mechanical Ventilation at Intermountain Healthcare Hospitals (Intermountain Medical Center = IMC, Utah Valley = UV, McKay Dee = MK, Dixie = DX, and LD = LDS Hospital).

[figure not shown]

Figure 4: An example of the weaning protocol that will be used in this study.

[figure not shown]
[figure not shown]

Figure 5: Process Flow Map for Supporting the Weaning Protocol

Rules for I Centra Ventilator Protocol

efi.			

- □ BWP: Body weight predicted (formula below)
 - \circ Males: PBW (kg) = 50 + 2.3[height (inches) -60]
 - \circ Females: PBW (kg = 45.5 + 2.3 [height (inches) -60]
- □ ABG: arterial blood gas
- □ VR: respiratory rate (breaths per minute)
- □ VT: tidal volume (milliliters)
- □ VE: minute volume (liters per minute)
- □ CMV: continuous mandatory ventilation
- □ VC: Volume Control
- □ PEEP: positive end expiratory pressure (cmH2O)
- ☐ Measured Pplat: actual measured plateau pressure

General:

- ☐ If the PBW does not appear or is too small or too large, check the height and gender in the computer they could be entered wrong or not at all.
- ☐ The protocol will not generate new instructions if it has been 2 or more hours since a complete ventilator assessment has been entered.
- □ Always do a ventilator assessment before drawing an ABG.
- ☐ Check for typos. The computer relies on accurate and timely charting.
- ☐ The protocol will run off arterial blood gas or oxygen saturation measured by the pulse oximeter.
- □ Protocol suspensions can be entered proactively or retroactively.
- □ Suspend the protocol when the patient will be receiving a procedure, traveling, going to surgery or hyperbaric.
- ☐ Unsuspend the protocol when back in the unit
- ☐ Enter at the previous settings
- ☐ Enter at the current settings charted (patient may have different needs after the procedure)
- The protocols are orders. Deviation from the protocol requires a physician order.

ABG Recommended For:

□ Change in Mode.

ABG Required For:

- □ 10% change in VT setting.
- □ Change in VR setting if patient is not assisting.
- Receive ventilation protocol instructions.

Ventilation:

- ☐ The low range for the set ventilatory rate is 6 breaths per minute for all protocols.
- □ Ventilation instructions are only given after an ABG.
- ☐ The protocol will set a back up VR if the patient is breathing over the set rate. Backup VR is based on a calculated VE goal.
- □ Set VT at 6ml/kg PWB
- □ VE goal = Current VE *(PaCO2/50 * HCO3-/24)

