☐ Entry criteria for weaning:

□ Without neuromuscular blockade

□ Weaning assessment will be attempted every 4 hours.

 \Box Peep < = 10 cmH2O

 \Box Total VR > set VR

 \Box FiO2 < = .5

	Backup set $VR = VE$ goal / set VT
	Volume control ventilation will be required unless FiO2 <= 0.5 and PEEP <= 10cmH2O, then the
	patient can be evaluated for pressure support weaning.
	Tidal Volume (VT) Goal is 6 ml / kg / PBW
	Measure and record inspiratory plateau pressure (Pplat) with every ventilator assessment and after
	changes in VT and PEEP.
	If Pplat is > 30 cmH2O an ABG is recommended to determine if a VT reduction is indicated.
	If unable to measure a Pplat when in PRVC, change the mode to A/C for 2 to 3 minutes. Measure the
	Pplat. Return the patient to previous mode.
	Do not increase ventilator rate (VR) above 35 bpm.
	Do not decrease VT below 4 ml/kg
	If the patient is not over breathing the set rate do not decrease VT and VR at the same time.
Oxy	ygenation:
	The protocol will not decrease PEEP for 6 hours after it has been increased.
	If PEEP is > 10 cmH2O, do not decrease > 2cmH2O every 2 hours.
	If the SpO2 or PaO2 fall below the target ranges after a decrease in FiO2 and/or PEEP and it has been
	less than 30 minutes, the patient will be returned to the previous FiO2 and PEEP settings.
	Each subsequent repeat of therapy reduction followed by therapy increase will result in waiting periods
	(4, 8, and 24 hours).
Nig	tht time:
	Night rests on CMV will start at 22:00 and end at 06:00 when ordered.
We	aning:
	Weaning may occur 24 hours a day.
	Weaning may be initiated at any time.

Table B.1. Tidal Volumes from Predicted Body Weight from Height and Gender

HEIG	ΗΤ	PBW	4 mi	5 m i	6 m l	7 m l	8 mi
4' 0" (4	48)	17.9	72	90	107	125	143
4' 1" (4	49)	20.2	81	101	121	141	162
4' 2" (50)	22.5	90	113	135	158	180
4' 3" (51)	24.8	99	124	149	174	198
4' 4" (52)	27.1	108	136	163	190	217
	53)	29.4	118	147	176	206	235
4' 6" (54)	31.7	127	159	190	222	254
4' 7" (55)	34	136	170	204	238	272
4' 8" (56)	36.3	145	182	218	254	290
4' 9" (57)	38.6	154	193	232	270	309
4' 10" (58)	40.9	164	205	245	286	327
4' 11" (59)	43.2	173	216	259	302	346
	60)	45.5	182	228	273	319	364
5' 1" (0	61)	47.8	191	239	287	335	382
5' 2" (0	62)	50.1	200	251	301	351	401
5' 3" (63)	52.4	210	262	314	367	419
	64)	54.7	219	274	328	383	438
	65)	57	228	285	342	399	456
5' 6" (6	66)	59.3	237	297	356	415	474
5' 7" (67)	61.6	246	308	370	431	493
5' 8" (6	68)	63.9	256	320	383	447	511
5' 9" (69)	66.2	265	331	397	463	530

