7.15 – 7.29 and VR < 35 bpm (measured rate)	19. ↑ VR by 20% increments ^a ↓ VT by 1 ml/kg	20. ↑ VR by 20% increments ^a ↓ VT by 1 ml/kg	21. ↑ VR by 20% increments ^a ↓ VT by 1 ml/kg	22. ↑ VR by 20% increments ^a	23. ↑ VR by 20% increments ^a	24. ↓ VT by 1 ml/kg ↑ VR by 20% increments ^a	25. ↑ VR by 20% increments ^a ↑ VT by 1 ml/kg	26. ↑ VR by 20% increments ^a	27. ↑ VR by 20% increments ^a
7.15 – 7.29 and VR = 35 bpm (measured rate)	28. ↓ VT by 1 ml/kg Check with MD to consider Bicarb	29. ↓ VT by 1 ml/kg Check with MD to consider Bicarb	30. ↓ VT by 1 ml/kg Check with MD to consider Bicarb	31. Check with MD to consider Bicarb	32. Check with MD to consider Bicarb	33. ↓ VT by 1 ml/kg Check with MD to consider Bicarb	34. ↑ VT by 1 ml/kg Check with MD to consider Bicarb	35. Check with MD to consider Bicarb	36. ↓ VT by 1 ml/kg but do not ↓ < 4 ml/kg Check with MD To consider Bicarb
< 7.15 and VR < 35 bpm (measured rate)	37. ↑ VR by 20% increments Check with MD to consider Bicarb	38. ↑ VR by 20% increments Check with MD to Consider Bicarb	39. ↑ VR by 20% increments Check with MD to Consider Bicarb	40. ↑ VR by 20% increments Check with MD to Consider Bicarb	41. ↑VR by 20% increments Check with MD to Consider Bicarb	42. ↓ VT by 1 ml/kg Check with MD to consider Bicarb	43. ↑ VR by 20% increments ^a ↑ VT by 1 ml/kg Check with MD to consider Bicarb	44. ↑ VR by 20% increments Check with MD to Consider Bicarb	45. ↑ VR by 20% increments Check with MD to Consider Bicarb
< 7.15 and VR = 35 bpm (measured rate)	46. Check with MD to consider Bicarb prior to ↑ VT by 1 ml/kg	47. Check with MD to consider Bicarb prior to ↑ VT by 1 ml/kg	48. Check with MD to consider Bicarb prior to ↑ VT by 1 ml/kg	49. Check with MD to consider Bicarb prior to ↑ VT by 1 ml/kg	50. Check with MD to consider Bicarb prior to ↑ VT by 1 ml/kg	51. Check with MD to consider Bicarb prior to ↑ VT by 1 ml/kg		53. Check with MD to consider Bicarb prior to ↑ VT by 1 ml/kg	54. Check with MD to consider Bicarb prior to ↑ VT by 1 ml/kg

$PaO_2 < 50 \text{ or } SpO_2 < 85\%$

(Use PaO₂ if available, only use SpO₂ if PaO₂ not available)

When PaO_2 or SpO_2 are in this low range, repeated sequential adjustments may be made as guided by the cells in the table until adequate oxygenation with a $SpO_2 \ge 88\%$ is achieved

PEEP	FiO ₂ = .3	$FiO_2 = .4$	FiO ₂ = .5	$FiO_2 = .6$	$FiO_2 = .7$	$FiO_2 = .8$	FiO ₂ = .9	$FiO_2 = 1.0$

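### As printed, the minute-ventilation goal multiplies by bicarbonate instead of dividing, so the backup rate moves the wrong way in metabolic acidosis and alkalosis

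*Protocol*

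**What the plan says.** The relevant text is in the Protocol's appended Rules for iCentra Ventilator Protocol, under Ventilation. For a patient breathing above the set rate, the computer sets a backup rate: "Backup VR is based on a calculated VE goal". The goal is given as "VE goal = Current VE *(PaCO2/50 * HCO3-/24", and the closing bracket follows directly. The rate is then "Backup set $VR = VE$ goal / set VT". VT is set at 6 ml/kg predicted body weight (PBW). The set rate is bounded below ("The low range for the set ventilatory rate is 6 breaths per minute for all protocols") and may not be raised above 35.

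Table B.2 in the same appendix gives the stepwise responses to pH and plateau pressure. At VT 6 ml/kg and plateau pressure up to 30 cm H2O, it raises the rate at pH 7.15–7.29 ("22. ↑ VR by 20% increments", and likewise cell 23). It makes no change at 7.30–7.45 and lowers the rate by 20% above 7.45 (cells 4 and 5).

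On the standing of these instructions, the General rules say: "The protocols are orders. Deviation from the protocol requires a physician order".

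**The concern.** The backup rate is proportional to the VE goal, so any error in the goal passes straight to the ventilator setting. Read as printed, the goal falls as bicarbonate falls and rises as bicarbonate rises. A patient with metabolic acidosis needs more ventilation to hold pH, and a patient with metabolic alkalosis needs less, so the bicarbonate term points the wrong way in both.

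In acidosis, the backup rate is what the patient receives if spontaneous drive fails, and the printed rule sets that floor low when ventilation matters most. In alkalosis, the printed rule can put the backup rate above the patient's own rate and drive pH further up.

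There is also a consequence for the study. Specific Aim 4 measures compliance with protocol instructions, so a clinician who rightly departs from this rule could be counted as non-compliant.

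**Working it through.** The Protocol states no numerical result for this rule, so there is no figure to reproduce. The check evaluates the formula and compares its direction with Table B.2.

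**Inputs from the Protocol:** the VE-goal formula, the backup-rate formula, VT 6 ml/kg PBW, and rate limits of 6 and 35/min (Ventilation rules); the pH bands and rate changes (Table B.2).

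**Assumed for illustration:** VE 12 L/min; PBW 70 kg, so VT = 6 × 70 = 420 mL; VE × PaCO2 constant (fixed CO2 production and dead space); pH = 6.1 + log10(HCO3 / (0.03 × PaCO2)).

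**1. The two factors applied to current VE**

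- Printed: (PaCO2/50) × (HCO3/24) = PaCO2 × HCO3 / 1,200.
- Divided: (PaCO2/50) / (HCO3/24) = 24 × PaCO2 / (50 × HCO3), which equals 10^(7.304 − pH).
- Printed / divided = (HCO3/24)² at any PaCO2: 0.25 at HCO3 12, 1 at HCO3 24, 2.25 at HCO3 36.

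The divided factor is a function of pH alone: above 1 below pH 7.304 and below 1 above it. The printed factor has no such property.

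**2. Where each rule settles.** With VE × PaCO2 constant, the goal equals current VE when the factor is 1.

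- Printed: PaCO2 = 1,200 / HCO3. At HCO3 12 this is PaCO2 100, pH 6.70. At HCO3 36 it is PaCO2 33.3, pH 7.66.
- Divided: PaCO2 = 50 × HCO3/24. At HCO3 12, 24 and 36 this is PaCO2 25, 50 and 75, each pH 7.30.

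A target of 7.30 is the lower edge of Table B.2's no-change band. No clinician would aim for pH 6.70 or 7.66. The constants 50 and 24 make sense together only in the divided form.

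**3. Worked gases (VE 12 L/min, VT 0.42 L)**

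| | PaCO2 30, HCO3 12 | PaCO2 50, HCO3 36 | PaCO2 80, HCO3 32 |
|---|---|---|---|
| pH | 7.22 | 7.48 | 7.22 |
| Table B.2 direction | rate up | rate down | rate up |
| Printed factor | 30 × 12 / 1,200 = 0.30 | 50 × 36 / 1,200 = 1.50 | 80 × 32 / 1,200 = 2.13 |
| Printed goal, L/min | 3.6 | 18.0 | 25.6 |
| Printed backup rate, /min | 8.6 | 42.9 (cap 35) | 61.0 (cap 35) |
| Divided factor | 1.20 | 0.667 | 1.20 |
| Divided goal, L/min | 14.4 | 8.0 | 14.4 |
| Divided backup rate, /min | 34.3 | 19.0 | 34.3 |

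If every breath is at set VT, the patient's own rate is 12 / 0.42 = 28.6/min. The third column is a respiratory acidosis, where both forms go the right way.

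**4. Sensitivity to the assumed VE.** For PaCO2 30, HCO3 12 and VE from 8 to 14 L/min:

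- Printed: 0.30 × 8 = 2.4 and 0.30 × 14 = 4.2 L/min, giving 5.7 (floor 6) to 10.0/min.
- Divided: 1.20 × 8 = 9.6 and 1.20 × 14 = 16.8 L/min, giving 22.9 to 40.0/min (cap 35).

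**5. Direction over a grid.** On whole-number values of HCO3 8–44 and PaCO2 20–90, the printed rule lowers VE at 677 of 1,303 points with pH below 7.295 and raises it at 336 of 736 points with pH above 7.45. The divided rule does so at none of either. These are grid points, not patient frequencies.

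**The case against.** The strongest objection is that the text may have been damaged in reading. Nearby lines in the same appendix are visibly garbled, and the printed outer bracket does no work, which suggests that an inner bracket or stacked fraction was lost. This cannot be ruled out from the text alone. But the line is complete with balanced brackets, and nothing elsewhere in the Protocol corrects it. The point therefore holds for the text as printed, subject to a look at the source page.

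A second objection is that the formula sets only a backup rate for patients already over-breathing, and the Protocol does not say whether Table B.2 also governs them. That weakens the claim of a direct contradiction with Table B.2 but not the acid-base argument, which stands alone. It is also true that in acidosis a low backup rate does no harm while the patient keeps triggering. Harm needs drive to fail, which is the event a backup rate exists for. In alkalosis no such failure is needed: the capped 35/min already exceeds the patient's 28.6/min.

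The limits of 6 and 35 bound the rate without correcting its direction; 8.6/min passes both. Physicians may decline the order set (Study Design; Significance), which reduces exposure, but once it is in use its instructions are orders.

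Two further cautions stand. The worked gases are large deviations: at HCO3 20 to 28 the printed goal is only about 0.69 to 1.36 times the divided one, and the Protocol gives no distribution of bicarbonate. And the target of pH 7.30 is inferred from the constants; no passage states it.

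**Conclusion.** The formula is wrong as printed. Its multiplier is a product of PaCO2 and HCO3 where acid-base balance requires a ratio. The goal falls below current VE when pH is under 7.30 and PaCO2 × HCO3 is under 1,200, and rises above it when pH is over 7.45 and the product is over 1,200. The error is a factor of (HCO3/24)²: a fourfold understatement at HCO3 12, a 2.25-fold overstatement at HCO3 36, and none at 24.

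The direction and this ratio need no assumption about VE or body weight; the rates per minute do. Confidence is medium, because one slash or bracket on the source page decides the matter. The consequence is confined to the safety and specification of the intervention. Sample size, alpha and the analysis are unaffected.

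**What to change.** 1. Check the source page and the rule as coded in iCentra. If both already divide by the bicarbonate term, only the document text needs correcting.
2. If the text stands as shown, replace it with `VE goal = current VE × PaCO2 / (50 × HCO3/24)`, subject to confirmation by the clinical owners that pH 7.30 is the intended target and that a backup rate above the patient's own rate is acceptable in acidosis.
3. Keep the existing limits of 6 and 35/min on the result.
4. Test the code on low- and high-bicarbonate gases. With VE 12 L/min and VT 420 mL, PaCO2 30/HCO3 12 should return 34.3/min and PaCO2 50/HCO3 36 should return 19.0/min. A gas at HCO3 24 cannot tell the two forms apart.

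The cost is one term in the rules document and the code, plus a short test before go-live.

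### Ventilation Table B.2, cell 42: as printed, it lowers tidal volume at pH below 7.15 and gives no rate increase although the rate is still below its cap

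*Protocol*

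**What the plan says.** The instructions are in the protocol's Rules for I Centra Ventilator Protocol, Table B.2, which crosses pH and measured rate (rows) with VT and Pplat (columns). Cell 42 reads "42. ↓ VT by 1 ml/kg Check with MD to consider Bicarb".

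Two cells in the same column (VT 6 ml/kg, Pplat > 30) are the natural comparators:

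- pH 7.15–7.29 with VR < 35: "24. ↓ VT by 1 ml/kg ↑ VR by 20% increments".
- pH 7.15–7.29 with VR = 35: "33. ↓ VT by 1 ml/kg Check with MD to consider Bicarb".

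The general rules set the frame. On rate: "Do not increase ventilator rate (VR) above 35 bpm". On high plateau pressure: "If Pplat is > 30 cmH2O an ABG is recommended to determine if a VT reduction is indicated". On timing: "Ventilation instructions are only given after an ABG". On status: "The protocols are orders. Deviation from the protocol requires a physician order". The list of events that require an ABG includes a "10% change in VT setting".

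**The concern.** The row holding cell 42 is defined by a rate that can still go up. Everywhere else in the table where the patient is acidotic and the rate is below 35, the instruction includes a rate increase. Cell 42 does not, and it also lowers VT, so the ventilator is set to deliver less to one of the most acidotic groups. A patient with the same VT, Pplat and rate condition but milder acidosis (cell 24) gets the rate increase.

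The table is written as orders, and the Significance section makes the computerized protocol the default for intubated patients. A patient who is not breathing above the set rate would stay on the reduced ventilation until the next ABG produces a new instruction. What is at stake is patient safety, not inference.

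**Working it through.** **Comparison of cells.** All entries are from Table B.2.

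1. Cells with pH < 7.30 and VR < 35 are 19–27 and 37–45: 9 + 9 = 18. Seventeen raise VR; cell 42 does not.
2. Of these 18, five cut VT: 19, 20, 21, 24 and 42. The first four pair the cut with a rate rise, and all four are at pH 7.15–7.29.
3. Cells at pH < 7.15 are 37–54, which is 18. Cell 52 is blank in the available text, leaving 17 printed. Cell 42 is the only one that cuts VT. Cells 39 and 45, the other two Pplat > 30 cells in its row, raise VR and leave VT alone. Cell 51, in its own column with VR = 35, has the physician consulted before VT is *raised*.
4. Down the same column at pH 7.15 or above, cells 6, 15, 24 and 33 all cut VT.
5. Apart from its number, cell 42 has the same wording as cell 33, where the rate is already 35 and cannot rise.

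Cell 42 therefore departs from its neighbours in two ways: the missing rate rise and, at this pH, the VT cut.

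**Size.** The protocol gives no figure to reproduce. For a patient not breathing above the set rate r, set minute ventilation is VT × r. Inputs from the table and rules: VT falls from 6 to 5 ml/kg, one rate step is 20%, and the cap is 35 bpm.

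- As printed: 5r / 6r = 0.833, a change of −16.7%.
- Rate step added, cut kept: (5/6) × min(35, 1.2r) / r.
- Rate step added, cut dropped: min(35, 1.2r) / r.

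The cap begins to bind at r = 35 / 1.2 = 29.2.

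| Set rate r | As printed | Cut kept, one step | Cut dropped, one step |
|---|---|---|---|
| up to 29 | −16.7% | 0.0% | +20.0% |
| 30 | −16.7% | −2.8% | +16.7% |
| 32 | −16.7% | −8.9% | +9.4% |
| 34 | −16.7% | −14.2% | +2.9% |

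With the cut kept, the rate step recovers all 16.7 points up to a rate of 29 but only 16.7 − 14.2 = 2.5 points at 34.

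These figures assume a single 20% step. The table speaks of increments in the plural, and the footnote marked on cell 24's rate step has no text in the available copy. If steps may be repeated, three from r = 20 give 20 × 1.2³ = 34.6, still below the cap. With the cut kept, the ratio is then (5/6) × 1.728 = 1.44, or +44%.

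**The case against.** **The cell may be damaged by text extraction.** Cell 52 is blank, footnote a has no text, and some PEEP entries in the later oxygenation tables lack their number. A lost line in cell 42 cannot be excluded. Against that, the cell is numbered, in sequence and reads as a complete order. This objection stands to the extent that the source must be checked first.

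**Safeguards limit the harm.** This largely stands.

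- The cell calls the physician. The call is about bicarbonate, however, and the other eight cells in the row make the same call and still raise VR.
- The VT change is 1/6 = 16.7%, above the 10% that requires an ABG.
- After the cut, the applicable cells are 43–45 (or 25–27 if pH recovers to 7.15–7.29), and all raise VR.
- The backup-rate rule protects patients breathing above the set rate, but not a passive one.
- Physicians may decline the protocol.

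**The VT cut may be the error.** A reader might infer that the cut is right, because the column cuts VT elsewhere, and that only the rate step is missing. The document does not settle this. The column's other cuts are all at pH 7.15 or above, no other printed cell at pH < 7.15 cuts VT, and the Pplat rule recommends an ABG to decide on a reduction without ordering one. Even with a single rate step added, a cell that keeps the cut would be the only one in its row that does not raise set ventilation. Either plausible repair, however, includes the rate rise.

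**Conclusion.** The point holds for the cell as printed. Cell 42 omits a rate increase that every other acidotic cell with VR < 35 contains, and lowers set minute ventilation by 16.7% in a patient not breathing above the set rate. The 16.7% follows directly from the cell; the effect of a repair depends on the single-step assumption.

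Two stronger readings are not supported. The match with cell 33 suggests a copied entry but does not prove one. Nor does the cell threaten the trial's conclusions: it has no effect on the analysis of ventilator-free days, and the protocol does not say how many patients would reach it. This is a low-to-moderate safety correction, held with medium confidence because the source table has not been seen.

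**What to change.** Check cell 42 against the source table and the order logic built into iCentra. If it stands as printed, add a VR increase in 20% increments up to the 35 bpm cap, and keep the physician check for bicarbonate.

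The protocol clinicians should then decide, and record, which form they intend:

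- keep the 1 ml/kg VT cut, as in cell 24, to address the high plateau pressure; or
- drop it, as in cells 39, 41 and 45, so that set ventilation rises.

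The cost is one look-up, one clinical decision and one edited cell. Sample size, data collection and analysis are unchanged.
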